4.1 Overall Design

Study intervention

MRI prostate

Bi-parametric and multi-parametric MRI prostates can be performed using a 3.0 Tesla scanner with a pelvic phased array coil with or without contrast. MRI findings will be reported according to PI-RADS (Prostate Imaging-Reporting and Data Systems) v2.1 recommendations. (12) MRI will be reported by radiologists with experience in MRI prostate reporting. PI-RADS scores 3-5 will be regarded as suspicious, and targeted plus systematic biopsy will be performed.

Prostate biopsy

In patients with suspicious lesion found on MRI (identified as PI-RADS score 3-5 lesions on bp-MRI or mp-MRI), biopsies will be done via trans-perineal approach under general anesthesia with 3 cores of targeted biopsy from each lesion, alone with 3 cores of systemic biopsy from right and left lobes respectively.

In those without identified suspicious lesions on MRI, a standard 12-core systematic biopsy will be performed via trans-rectal approach under local anesthesia.

All biopsies will be performed by Urologists experienced in both targeted and systemic prostate biopsy. Targeted biopsies will be done by software-assisted MRI-USG fusion registration. Peri-biopsy antibiotics are given according to our clinical guidelines.

Post-biopsy management

Patients will be discharged after prostate biopsy when they can pass urine without significant gross hematuria, and clinically stable. They will be followed up in the clinic within 10 days after a biopsy to review pathology results and complications. All biopsies will be assessed by experienced Urogenital pathologists and reported according to the International Society of Urological Pathology (ISUP) consensus. (23) The study period ends after the first clinic follow-up.

[figure not shown]
In our medical research, we prioritize protecting participant privacy and confidentiality. We use unique research codes to anonymize personal details like names and IDs. The principal investigator keeps consultation results and diagnoses confidential, even in published research. Participants consent to have their records reviewed by authorized parties for legal and ethical compliance, with a promise of maintaining their anonymity. For safety, we may inform

participants' other doctors about their trial involvement to manage treatment interactions.

Overall, these steps ensure participant privacy and safety throughout the research.

Flow Chart (試驗流程圖) :

Figure 1. Study design

4.1 Number of Patients

evaluable number

The sample sizes of 148 in the **bp-MRI group** and 148 in the **mp-MRI group** achieve 80.145% power to detect a non-inferiority margin difference between the group proportions of -0.1000. The **mp-MRI group proportion** is 0.280. Under the null hypothesis of inferiority, the **bp-MRI proportion** is assumed to be 0.180. The power was computed for the case where the actual treatment group proportion is 0.280. The test statistic used is the one-sided Z test (unpooled), and the significance level of the test is 0.025. We have set the dropout rate at 20%, thus the bp-MRI group and mp-MRI group each consist of 185 individuals, resulting in a total enrolled number of 370 people. **We have set the dropout rate at 20%, thus the mp-MRI group and bp-MRI group each consist of 185 individuals, resulting in a total enrolled number of 370 people.**

enrolled number

We have set the dropout rate at 20%, thus the mp-MRI group and bp-MRI group each consist of 185 individuals, resulting in a total enrolled number of 370 people.

4.2 Schedule of Activities

Time-Event scheme(評估時程表):

	Screening	Imaging	Verification	Post-biopsy management
Category	Registration	MRI	Prostate biopsy	
Time frame	Day 1-14	Day 15-28	DAY 29-58	Day 59-68
Assessment				

Protocol: BMPFB Trial

Inform consent	✓			
History taking	✓			
PSA level	✓			
Digital Rectal Examination	✓			
Abnormal Ultrasound	✓			
Staging bp-MRI or mp-MRI		✓		
Biopsy			✓	
Hematuria				✓
Pathology report				✓

5. Study Population

5.1 Inclusion Criteria

Inclusion criteria:

1. Men \geq 50 years of age
2. Clinical suspicion of prostate cancer and indicated for prostate biopsy
3. Serum Prostate-specific antigen (PSA) between 4~20 ng/mL
4. Eligible for MRI study
5. Digital rectal examination \leq cT2 (organ-confined cancer)
6. Able to provide written informed consent.

5.2 Exclusion Criteria

Exclusion criteria:

1. Prior prostate biopsy in the 6 months before screening visit
2. Prior diagnosis of prostate cancer
3. Contraindicated to prostate biopsy: active urinary tract infection, failed insertion of transrectal ultrasound probe into rectum (abdominal perineal resection, anal stenosis), uncorrectable coagulopathy, antiplatelet or anticoagulant which cannot be stopped (continue low-dose aspirin before and after biopsy is permitted)
4. Contraindicated to MRI study: contrast medium allergy, claustrophobia, or other contraindications (e.g.: intra-abdominal metal foreign bodies).
5. Patients without histological results of prostate biopsies due to patient refusal for biopsy or loss of follow up before biopsy being done
6. Patients have prior treatments for prostate cancers or any kinds of hormone therapy, immunotherapy, chemotherapy, radiation therapy of the pelvic cavity.
7. Patients' withdrawal of informed consents of this study

5.3 Withdrawal criteria

1. Patients could not complete the scheduled MRI examinations
2. MRI images of insufficient quality to localized csPCA or to exclude the presence of csPCA

6. Treatments

Not Applicable

6.1 Treatment Administration

Not Applicable

6.2. Concomitant Therapy

Not Applicable

7. Efficacy Assessments

Not Applicable

8. Safety Assessments

Allergic Reactions: Some individuals may have allergic reactions to MRI contrast agents (usually containing gadolinium). Before administering the contrast agent, medical staff will inquire about the patient's allergy history to determine the risk of an allergic reaction.

Renal Function: Contrast agents can affect renal function. Patients with renal impairment

require a renal function assessment before undergoing an MRI scan with gadolinium-based contrast agents.

9. Adverse event reporting

The PI [name] will report SAEs to the IRB of Chang Gung Medical Foundation according to the Serious Adverse Event Reporting Procedures and Guidelines as posted in the Clinical Trials Resource on the website of Chang Gung Medical Foundation IRB. SAE reports to the IRB should include the following information when calling the Medical Monitor:

- Date and time of the SAE
- Date and time of the SAE report
- Name of reporter
- Call back phone number
- Affiliation/Institution conducting the study
- Protocol number
- Title of protocol
- Description of the SAE, including attribution to drug and expectedness

9.1 Definitions and reports of Adverse Events

All adverse events that occur after the informed consent is signed (including run-in) must be recorded on the adverse event CRF (paper and/or electronic) whether or not related to study agent. AE Data Elements including:

- AE reported date
- AE Verbatim Term
- CTCAE Term (v 5.0)
- Event onset date and event ended date
- Severity grade
- Attribution to study agent (relatedness)
- Whether or not the event was reported as a Serious Adverse Event (SAE)
- Action taken with the study agent
- Outcome of the event
- Comments

Identify the adverse event using the NCI Common Terminology Criteria for Adverse Events (CTCAE) version 5.0. The CTCAE provides descriptive terminology and a grading scale for each adverse event listed.

AEs will be assessed according to the CTCAE grade associated with the AE term. AEs that do not have a corresponding CTCAE term will be assessed according to their impact on the participant's ability to perform daily activities as follows:

Grade	Severity	Description
1	Mild	
• Barely noticeable, does not influence functioning• Causing no limitations of usual activities

2	Moderate	
 • Makes participant uncomfortable, influences functioning • Causing some limitations of usual activities
3	Severe	
 • Severe discomfort, treatment needed • Severe and undesirable, causing inability to carry out usual activities
4	Life threatening	
 • Immediate risk of death • Life threatening or disabling
5	Fatal	
 • Causes death of the participant

The possibility that the adverse event is related to study drug will be classified as one of the following: not related, unlikely, possible, probable, definite.

DEFINITION of Serious Adverse Events: ICH Guideline E2A and GCP of Taiwan define serious adverse events as those events, occurring at any dose, which meet any of the following criteria:

- Results in death
- Is life threatening (Note: the term life-threatening refers to an event in which the patient was at risk of death at the time of the event; it does not refer to an event which hypothetically might have caused death if it were more severe).
- Requires inpatient hospitalization or prolongation of existing hospitalization
- Results in persistent or significant disability/incapacity
- Is a congenital abnormality/birth defect
- Events that may not meet these criteria, but which the investigator finds very unusual and/or potentially serious, will also be reported in the same manner.

9.2 Adverse event follow-up

All AEs, including lab abnormalities that in the opinion of the investigator are clinically significant, will be followed according to good medical practices and documented as such. Site staff should send follow-up reports as requested when additional information is available. Additional information should be entered on the IRB of Chang Gung Medical Foundation of SAE form in the appropriate format. Follow-up information should be sent to Chang Gung Medical Foundation IRB as soon as possible according to IRB's Serious Adverse Event Reporting Procedures and Guidelines.

10. Criteria for the termination of the trial

Following CGMH's Management of Study Termination guideline, the trial shall be terminated by the investigator or the CGMH IRB when deemed necessary after evaluation. Incidents that may cause the termination of the trial include the encounter of life-threatening AE, fatal AE, etc. The PI will send in an application via CGMH HRPMS system to file for the termination of the trial.

11. Statistical Considerations

11.1 Sample size Determination

The sample sizes of 148 in the **bp-MRI group** and 148 in the **mp-MRI group** achieve 80.145% power to detect a non-inferiority margin difference between the group proportions of -0.1000. The **mp-MRI group proportion** is 0.280. Under the null hypothesis of inferiority, the **bp-MRI proportion** is assumed to be 0.180. The power was computed for the case where the actual treatment group proportion is 0.280. The test statistic used is the one-sided Z test (unpooled), and the significance level of the test is 0.025. We have set the dropout rate at 20%,

thus the bp-MRI group and mp-MRI group each consist of 185 individuals, resulting in a total enrolled number of 370 people. We have set the dropout rate at 20%, thus the mp-MRI group and bp-MRI group each consist of 185 individuals, resulting in a total enrolled number of 370 people.

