There are estimated 600+ patients diagnosed and treated as prostate cancer in our institute every year. We performed about 800+ prostate biopsies in our hospital per year. Assuming 40-50% of men agree recruitment to this study, about 200-250 men will be recruited per year, and the recruitment for the whole study should complete in 24 months, and the study to complete in 30 months.

Study intervention**MRI prostate**

Bi-parametric and multi-parametric MRI prostates can be performed using a 3.0 Tesla scanner with a pelvic phased array coil with or without contrast. MRI findings will be reported according to PI-RADS (Prostate Imaging-Reporting and Data Systems) v2.1 recommendations. (12) MRI will be reported by radiologists with experience in MRI prostate reporting. PI-RADS scores 3-5 will be regarded as suspicious, and targeted plus systematic biopsy will be performed.

Prostate biopsy

In patients with suspicious lesion found on MRI (identified as PI-RADS score 3-5 lesions on bp-MRI or mp-MRI), biopsies will be done via trans-perineal approach under general anesthesia with 3 cores of targeted biopsy from each lesion, alone with 3 cores of systemic biopsy from right and left

lobes respectively.

[figure not shown]
In those without identified suspicious lesions on MRI, a standard 12-core systematic biopsy will be performed via trans-rectal approach under local anesthesia.

All biopsies will be performed by Urologists experienced in both targeted and systemic prostate biopsy. Targeted biopsies will be done by software-assisted MRI-USG fusion registration. Peri-biopsy antibiotics are given according to our clinical guidelines.

Post-biopsy management

Patients will be discharged after prostate biopsy when they can pass urine without significant gross hematuria, and clinically stable. They will be followed up in the clinic within 10 days after a biopsy to review pathology results and complications. All biopsies will be assessed by experienced Urogenital pathologists and reported according to the International Society of Urological Pathology (ISUP) consensus. (23) The study period ends after the first clinic follow-up.

Figure 1. Study design

Concomitant Treatments : 不適用

1. Concomitant Therapy :
2. Prohibited Therapy :

Statistical Methods :

1. Main study Hypothesis : Equality Superiority Non-inferiority
 Equivalence Other _____
2. Estimated Sample Size : 整個試驗預計納入人數 370，整個試驗可評估人數 370
 本中心預計納入人數 370，本中心可評估人數 370

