Patients who are suspicious of prostate cancers with abnormal digital examination, or abnormal ultrasound and having a pre-MRI and were scheduled to receive prostate biopsy will be enrolled in this study. Patients will be randomized in a 1:1 manner to bp-MRI and mp-MRI. Patients with clinical suspicion of prostate cancer on MRI with PI-RADS (Prostate Imaging-Reporting and Data System, version 2.1) [18] score 3-5 will be arranged to receive MRI-Ultrasound fusion biopsy for targeted and systemic biopsy. Patients who have no suspicious lesions found on MRI will receive standard

Protocol: BMPFB Trial

systemic biopsy only instead. The study flowchart is provided in Figure 1. The detection rates of csPCa will be compared between arms. The study hypothesis is that bp-MRI has similar detection rate for csPCa comparing to mp-MRI.

To formulate the randomization codes and distribution process, we first plan to recruit a total of 370 participants. Then, we choose a block size of 4 to maintain balance between groups while reducing the predictability of the assignment sequence. Utilizing the block randomization method, we generate random codes for each block to ensure an equal number of participants in each treatment group. Subsequently, a complete table of random codes is created using a random number generator, serving as the basis for participant assignment.

As participants enter the study, they will be assigned to the respective groups according to the sequence of the random code table, namely the bp-MRI group or the mp-MRI group. This process not only ensures the randomness of the assignments but also helps maintain the fairness and transparency of the research. After each assignment, we record the detailed information of the participants and the group they are assigned to, ensuring the traceability and transparency of the entire process.

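### The stated 80.145% power does not follow from the stated inputs: 148 evaluable men per arm at 28% versus 28% gives about 48%

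*Combined protocol and SAP*

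**What the plan says.** Section 11.1 gives a complete set of inputs, and Section 4.1 (Number of Patients) repeats them:

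- Evaluable size: "The sample sizes of 148 in the bp-MRI group and 148 in the mp-MRI group".
- Power and margin: these sizes "achieve 80.145% power to detect a non-inferiority margin difference between the group proportions of -0.1000".
- Control rate: "The mp-MRI group proportion is 0.280".
- Null value for the experimental arm: "the bp-MRI proportion is assumed to be 0.180", that is, 0.28 minus the 0.10 margin.
- Value at which power is evaluated: "The power was computed for the case where the actual treatment group proportion is 0.280".
- Test: "The test statistic used is the one-sided Z test (unpooled), and the significance level of the test is 0.025".

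Allocation is equal (Section 4: "Patients will be randomized in a 1:1 manner to bp-MRI and mp-MRI"). A 20% dropout allowance takes 148 to 185 per arm, 370 in total. Section 4 states the hypothesis as similar csPCa detection by the two MRI types, and Section 11.2 states it as non-inferiority of bp-MRI.

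The synopsis, under Estimated Sample Size, gives 370 as the planned enrolment and also as the evaluable number for the whole trial: "整個試驗可評估人數 370". Section 4.1 labels 148 per arm, 296 in total, as evaluable.

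**The concern.** With a control rate near 28%, a 10-point margin and no true difference, 148 per arm is small for a one-sided 0.025 test: the standard error of the difference is about half the margin. A power of 80% needs the distance to the margin to be about 2.8 standard errors (1.96 + 0.84).

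This figure is the only justification given for the trial's size, and it concerns the primary hypothesis. If it is wrong, the IRB and funder have approved a trial with a materially lower chance of success than stated. A confidence interval that crosses the margin could also be taken as evidence against bp-MRI when the trial was simply too small to decide.

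**Working it through.** **Inputs (Section 11.1).** n = 148 per arm; p_mp = 0.28; true p_bp = 0.28; margin 0.10; one-sided alpha 0.025 (z = 1.96); unpooled variance.

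**Formula.** Power = Φ[(0.10 + p_bp − p_mp)/SE − 1.96], with SE = √{[p_bp(1 − p_bp) + p_mp(1 − p_mp)]/n}.

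**1. Attempt to reproduce the stated figure.**

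- SE = √(2 × 0.28 × 0.72/148) = 0.0522
- 0.10/0.0522 = 1.916
- Power = Φ(1.916 − 1.960) = **48.2%**, against 80.145% stated
- Exact binomial enumeration of the same test: 48.4%

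**2. Other methods and readings, both rates 0.28 unless noted.**

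| Variant | Power |
|---|---|
| Null-variance standard error, n = 148 | 53.7–53.9% |
| Pooled formula for 0.28 versus 0.18, n = 148 | 53.4% |
| Continuity correction, n = 148 | 43.1% |
| 0.025 read as two-sided, n = 148 | 37.2% |
| One-sided alpha 0.05, n = 148 | 60.7% |
| One-sided alpha 0.10, n = 148 | 73.7% |
| Stated alpha, n = 185 (all 370 evaluable) | 57.2% |
| One-sided alpha 0.10, n = 185 | 80.5% |

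Only the last row comes near 80%. It uses neither the stated alpha nor the stated evaluable number, and it does not give 80.145%.

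**3. What does give 80.145%.** Keep every stated input and change only the true bp-MRI rate to 0.33:

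- SE = √[(0.33 × 0.67 + 0.28 × 0.72)/148] = 0.0534
- (0.10 + 0.05)/0.0534 = 2.807
- Power = Φ(2.807 − 1.960) = **0.80145**

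Solving for the bp-MRI rate returns 0.3300. At that rate 147 per arm gives 79.88%, so 148 is the smallest size that reaches 80%. Both the power and the sample size in the plan are therefore explained by 0.33.

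Changing one other input instead would require a margin of about 0.146, a one-sided alpha of about 0.143, a common rate of about 10.5%, or about 318 per arm. The plan states none of these.

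**4. Precision at the planned size.** The 95% CI half-width is 1.96 × 0.0522 = 10.2 points at an observed rate of 28% in both arms. That exceeds the 10-point margin, so an observed difference of exactly zero would not show non-inferiority.

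**5. Size needed on the stated inputs.**

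- n = (1.96 + 0.8416)² × 2 × 0.28 × 0.72/0.10² = 316.5, so 317 evaluable per arm
- 317/0.8 = 396.25, so 397 per arm, 794 enrolled

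**6. Dropout step.** 148/0.8 = 185. This part of the plan is correct.

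**7. Evaluable number.** 148 + 148 = 296 (Sections 4.1 and 11.1) against 370 (synopsis). Both cannot hold if 20% of 370 drop out.

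**The case against.** The arithmetic itself cannot be rebutted: every input is printed, and no other section corrects the figure. What can be contested is how far the consequences reach.

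- **The 0.33 explanation is an inference.** This stands. The match is close and specific, but the plan never mentions 0.33, and the error could have arisen in another way. The finding does not need the explanation, because 80.145% does not follow from what is printed.
- **Being more likely to fail than succeed depends on dropout.** This also stands as a condition. Under equality, power is 49.8% at 154 evaluable per arm and passes 50% at 155, which corresponds to dropout of about 16% (155/185 = 83.8% retained). At the plan's own 148 it is below one half; with nobody lost it is 57.2%.
- **A zero difference fails only at certain observed rates.** Correct. At 148 per arm the half-width is 10.1 points at a common observed rate of 27% but 9.99 points at 26%, so a zero difference would pass at 26% or lower. The statement applies at the plan's 28%.
- **Misreading of a failed result is speculative.** It is a risk, not something the documents show.
- **The synopsis discrepancy is separate and smaller.** It did not cause the power error, and taking 370 as evaluable does not rescue the figure.
- **Rewording does not repair the design.** True. It corrects what readers are told and leaves a non-inferiority trial with about 48% power under equality.

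**Conclusion.** The concern holds and must be fixed. On the plan's own inputs, power is 48.2% at 148 per arm, about 32 percentage points below the stated 80.145%; it is 57.2% if all 370 men are evaluable. No variance formula tried at the stated alpha brings it near 80%. The result rests only on numbers printed in Section 11.1 and on the test named there.

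The printed power is valid for a true bp-MRI rate of 0.33 with the other inputs unchanged. That would be a 5-point advantage for bp-MRI, which conflicts with both the stated 0.28 and the hypothesis of similar detection. That the calculation was actually run with 0.33 is likely but not proven.

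**What to change.** **Sections 4.1 (Number of Patients) and 11.1.** The sponsor should check the original calculation and then do one of the following:

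1. Keep 0.28 in both arms and state that 148 evaluable per arm gives about 48% power (about 57% if all 370 are evaluable); or
2. State that 80.145% assumes a true bp-MRI rate of 0.33, justify expecting bp-MRI to detect more csPCa than mp-MRI, and show power at 0.28 and at 0.33 side by side (48.2% and 80.1% at 148 per arm).

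In either case, list the size needed for 80% power under equality (317 evaluable per arm, 794 enrolled) so that the decision to stay at 370 is made knowingly.

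**Synopsis.** Change the evaluable number to 296, the number on which power is calculated, or explain why no dropout is expected.

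**Section 11.2.** It is advisable to add that failure to show non-inferiority will be reported as inconclusive unless the interval also excludes equality. The correction does not depend on this.

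**Cost.** The corrections are wording only and need no extra patients, but the stated power becomes less favourable. They fix the disclosure and leave the design as it is. Enlarging to 794 would take about 3.2 to 4.0 years at the synopsis's 200–250 recruits per year (794/250 and 794/200), against the 24 months planned.

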11.2 Planned Statistical methods of analysis

Statistical analysis

The primary objective of this study is to evaluate the csPCa detection in bp-MRI arm versus mp-MRI arm. We hypothesise that bp-MRI is non-inferior to mp-MRI in detecting csPCa. The baseline characteristics of the two groups will be compared. Continuous variables will be evaluated using the student's t-test and the Mann-Whitney U test. In contrast, categorical variables will be analysed using the Chi-squared and Fisher's exact tests, as applicable. The effect size and 95% CI will be presented for secondary outcomes, and a 2-sided p-value less than 0.05 will be considered statistically significant. All statistical analyses will be performed using SPSS v.24.0 (IBM Corp., Armonk, NY, USA).

